5.3 Randomization and Blinding

This study follows a randomized, double-blind, placebo-controlled design. Patients in Part A will be randomized via the Interactive Response Technology (IRT) system to 1 of 4 parallel treatment groups on Day 1 in a 1:1:1:1 ratio. However, prerandomization will occur within the IRT system at least 7 days prior to randomization. Patients in Part B will be randomized via the IRT system to 1 of 3 parallel treatment groups on Day 1 in a 1:1:1 ratio. Prerandomization is not applicable in Part B.

Both EYP001a and placebo will be provided as tablets for oral administration and will be identical in appearance.

Prerandomization/randomization information will be concealed from the Investigators and the patients until the end of the study, with the exception of an emergency situation involving a patient that required unblinding of the treatment assignment.

5.3.1 Stratification

Randomization will be stratified by statin use (yes, no) and T2DM status (yes, no) in Part A, and by statin use (yes, no) and LFC (stratification factor with 3 categories: LFC<16%, 16%≤LFC<22%, and 22%≤LFC) in Part B at screening. Randomization can occur after eligibility check on Day -3, at the earliest, and prior to dosing on Day 1 at the latest.

5.4 Breaking the Blind

Until formal conclusion of the study, patients, Investigators, and all clinical site personnel will remain blinded to treatment allocation, except in the event of a medical emergency that necessitates unblinding. In the event of a medical emergency, when knowledge of the patient's treatment assignment would influence the patient's clinical care, the clinical site will be able to unblind the patient via the IRT system. In the case of unblinding, the IRT system will send a blinded notification to study team members to let them know that a patient was unblinded.

In preparation for the DSMC meeting, Part A data were unblinded and analyzed by an independent statistician and presented to the DSMC. The study team remained blinded during this analysis. Due to the DSMC decision to update dosing arms, all Part A data were locked and unblinded data were sent to the unblinded Sponsor statistician.

When 50% of patients have completed the Week 8 visit in Part B, the DSMC will review all available primary and secondary endpoints according to the DSMC charter. The conclusions and recommendations of the DSMC will be shared blindly with the clinical sites.

5.5 Drug Supplies

5.5.1 Formulation and Packaging

The drug product will be supplied as immediate-release coated tablets for oral administration. Excipients include lactose monohydrate, microcrystalline cellulose, crospovidone, sodium lauryl sulfate, silicon dioxide, and magnesium stearate. Placebo tablets will appear identical to EYP001a.

For Part A, all study drug (EYP001a and placebo) will be packaged in blister packs and wallets. One wallet will contain 2 weeks of study drug (ie, 14 days of EYP001a or placebo) as per the randomization schedule. Morning and evening tablets will be clearly labeled.

For Part B, all study drug (EYP001a and placebo) will be packaged in blister packs and carton boxes. One box will contain 3 weeks of study drug (ie, 3 blister strips or 21 days of EYP001a or placebo) as per the randomization schedule.

5.5.2 Study Drug Preparation and Dispensing

For Part A, study drug will be dispensed as 100 and 200 mg tablets for oral administration at Weeks 0, 2, 4, and 8 by blinded clinical site personnel. Patients will receive enough study drug to last until the next visit.

For Part B, study drug will be dispensed as 100 and 200 mg tablets for oral administration at Weeks 0, 2, 4, 6, 8, and 10 by blinded clinical site personnel. Patients will receive enough study drug to last until the next visit.

5.5.3 Study Drug Administration

EYP001a is only available for oral administration. The study drug should be administered with noncarbonated water.

For Part A, patients will take 2 tablets in the morning during breakfast and 1 tablet in the evening during dinner.

For Part B, patients will take 1 tablet in the morning during breakfast.

On study visit days, patients should come fasted to the clinical site and take their morning dose during breakfast at the clinical site, following blood sample collection, except during intense PK/PD sampling on Days 1 and 14 of Part A, when dosing will occur with water only.

5.5.4 Treatment Compliance

In Part A, patient diaries will be reviewed to assess compliance throughout the study. In Parts A and B, the quantity of study drug dispensed to and returned by the patient will be counted. If the patient is not compliant with study drug intake, the Investigator should discuss this with the patient.

If study drug compliance drops below 80% at any given time during the Treatment Period, the Investigator or designee should discuss compliance with the patient and counsel the patient appropriately. Noncompliance includes missed doses in addition to taking the wrong dose. The Investigator must encourage compliance with the study drug and with the study procedures at all times.

5.5.5 Storage and Accountability

Study drug should be stored in a cool, dry place (15°C to 25°C or 59°F to 77°F) (stable from 5°C to 40°C, with 75% relative humidity).

The Investigator or appropriately trained designee will maintain an accurate record of the receipt of the study drug shipment, including the date and quantity received. Refer to the Pharmacy Manual for further information.

In addition, an accurate drug dispensing record will be kept that specifies the amount of study drug dispensed to each patient and the date of dispensing.

A drug accountability inventory record to account for all dispensing and return of any used and unused study drug must be maintained and available by the clinical site staff for inspection at any time. At the end of the study, the study drug will be reconciled, and copies of the complete record of study drug accountability will be provided to the Sponsor.

5.6 Prior and Concomitant Medications and/or Procedures

Unless medically warranted, all concomitant medications should remain stable from screening through the EOS Visit.

5.6.1 Excluded Medications and/or Procedures

Excluded medications and procedures include the following:

- Anticancer drugs, immunomodulators, and immunosuppressants within 90 days or 5 half-lives prior to screening, whichever is longer
- Drugs historically associated with NAFLD for >2 weeks in the year prior to screening (eg, amiodarone, methotrexate, systemic glucocorticoids, tetracyclines, tamoxifen, estrogens at doses greater than those used for hormone replacement, anabolic steroids, or valproic acid or other known hepatotoxins at the Investigator or Medical Monitor's discretion)
- Vitamin E (>400 IU/day), glitazones, glucagon-like peptide-1 receptor agonists, ursodeoxycholic acid, or obeticholic acid within 90 days prior to screening
- Agents (including herbal over-the-counter weight loss preparations) or medications known to significantly impact body weight within 90 days prior to screening (eg, sibutramine, phentermine, and orlistat)
- Bile acid sequestrants (eg, cholestyramine) or lipid-modifying agents (eg, fibrates or ezetimibe) other than rosuvastatin, atorvastatin, simvastatin, pravastatin, fluvastatin, or lovastatin
- Agents that are substrates for CYP2C8 or CYP2C9 and have a narrow therapeutic index (eg, warfarin)
- Prior or planned (during the study period) bariatric surgery (eg, gastroplasty or Roux-en-Y gastric bypass)
- Major surgery within 90 days prior to the first study drug administration

5.6.2 Restricted Medications and/or Procedures

Patients receiving statin therapy (rosuvastatin, atorvastatin, simvastatin, pravastatin, fluvastatin, or lovastatin are the only allowable statins) need to be on stable therapy for at least 90 days prior to the first administration of study drug. If LDL-C increases >10 mg/dL at Week 2, the statin dose may be increased and titrated up at the following visit if the LDL-C remains 5% above the baseline value.

For patients without statin therapy at baseline, if LDL-C increases $\geq 25\%$ from Day 1 to Day 14, rosuvastatin 20 mg QD will be introduced and titrated up to 40 mg QD at the following visit if LDL-C remains 5% above the baseline value.

Patients receiving other lipid-lowering treatments need to be on stable therapy for at least 90 days prior to the first study drug administration and must agree to remain on a stable regimen for their entire participation in the study. Patients with T2DM should be on a stable dose of antidiabetic medication for at least 90 days prior to screening and must agree to remain on a stable regimen for their entire participation in the study.

Close monitoring is required for comedication agents that are substrates for CYP2C8 or CYP2C9.

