6.3.3.3 Day 28 (Week 4)

The following procedures will be performed at Day 28 (Week 4):

- Record changes in concomitant medications.
- Perform brief physical examination.
- Measure body weight and calculate BMI.
- Measure waist and hip circumferences.
- Calculate WHR and WHtR.

- Collect vital signs (systolic and diastolic blood pressure, heart rate, respiratory rate, and body temperature) with the patient in the sitting position after 5 minutes of rest and before any blood draws.
- Administer the AUDIT-C test.
- Counsel on diet/lifestyle.
- Collect blood sample for the following:
 - Chemistry, hematology, coagulation, and lipid and metabolic profile.
 - Sparse PD (predose [fasting]).
 - Liver fibrosis and inflammation.
 - Sparse PK (predose [fasting]).
 - Plasma storage.
- Collect urine sample for urinalysis and pregnancy test. If the pregnancy test is positive, perform serum hCG test.
- Perform 12-lead ECG.
- Assess adverse events.
- Collect returned used/unused study drug and assess compliance.
- Dispense new study drug and provide dosing instructions.

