6.3.3.4 Day 42 (Week 6)

The following procedures will be performed at Day 42 (Week 6):

- Record changes in concomitant medications.
- Collect blood sample for the following:
 - Chemistry for assessment of ALT, AST, ALP, GGT, and total bilirubin.
- Assess adverse events.
- Collect returned used/unused study drug and assess compliance.
- Dispense new study drug and provide dosing instructions.

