9.8 Clinical Laboratory Evaluations

Clinical safety laboratory parameters will be measured or calculated at study visits specified in [Appendix A](#). Profiles for hematology, coagulation, serum chemistry, lipid and metabolic parameters, and urinalysis will be evaluated from samples collected after ≥ 6 hours of fasting (nothing by mouth except water). Further analysis of urine sediment or urine microscopy will be performed when there are any abnormalities on any of the following 3 dipstick results: leukocyte esterase, blood, or nitrite, and if judged clinically significant by the Investigator. See [Appendix B](#) for a complete list of laboratory analytes.

For women of childbearing potential, a serum hCG test will be performed at screening and the EOS and ET Visits. Urine hCG testing will be performed at visits specified in Appendix A. If a urine hCG test is positive, a serum hCG test will be performed.

Follicle-stimulating hormone level will be measured at screening to confirm postmenopausal state in women ≤ 55 years of age.

Anti-HBV, anti-HCV, and anti-HIV will be assessed at screening, and HCV RNA will be reflexively tested. Samples will be collected for central laboratory analysis except if viral serology data is already available in patient's medical history/records and obtained within 90 days prior to screening.

Plasma from blood samples obtained at screening and at study visits specified in Appendix A, including EOS and ET Visits, will be stored for protocol-related safety testing or exploratory analyses.

Blood sampling procedures, including information on blood volume, collection tubes, sample processing, storage, and shipping are provided in the Laboratory Manual.

The safety of statin coadministration will be assessed at study visits specified in Appendix A by monitoring CK levels.

Technical details on laboratory parameters (methods and commercial kit[s]) will be specified in the Laboratory Manual.

Additional laboratory testing may be required in response to adverse events and laboratory findings as described in the Clinical Safety Monitoring Plan ([Appendix E](#)). Laboratory abnormalities should be reported as an adverse event if any of the following is applicable:

- If an intervention is required as a result of the abnormality (such as a re-test being performed more than 1 time)
- If action taken with the study drug is required as a result of the abnormality

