k.	Vital signs include systolic and diastolic blood pressure, heart rate, respiratory rate, and body temperature and will be performed with the patient in the sitting position after 5 minutes of rest and before any blood draws. Clinical site staff will use a mercury sphygmomanometer or automatic blood pressure device with an appropriately sized cuff with the bladder centered over the brachial artery. Clinical site staff will record the arm used for the measurement and use the same arm throughout the study. Clinical site staff will measure and record the blood pressure. Blood pressure will be recorded to the nearest 2 mmHg mark on the manometer or to the nearest whole number on an automatic device. A blood pressure reading will be repeated 1 to 2 minutes later, and the second reading will also be recorded to the nearest 2 mmHg mark.										
l.	Patients with AUDIT-C scores ≥3 points at screening will receive the full AUDIT and will be excluded if they score ≥8 points on the full AUDIT. Patients with AUDIT-C scores <3 points will not receive the full AUDIT.										
m.	Can occur after eligibility check on Day -3 at the earliest and prior to dosing on Day 1 at the latest.										

- n. Anti-HCV, anti-HIV, and anti-HBV status will be assessed, and HCV RNA will be reflexively tested. Samples will be collected for central laboratory analysis except if viral serology data is already available in patient's medical history/records and obtained within 90 days prior to screening.
- o. Collected after ≥ 6 hours of fasting. See [Appendix B](#) for the complete list of clinical laboratory parameters.
- p. On Days 42 and 70 only ALT, AST, ALP, GGT, and total bilirubin will be measured.
- q. Urinalysis will be evaluated from samples collected after ≥ 6 hours of fasting. Further analysis of urine sediment or urine microscopy will be performed when there are any abnormalities on any of the following 3 dipstick results: leukocyte esterase, blood, or nitrite, and if judged clinically significant by the Investigator.
- r. For women of childbearing potential, a serum hCG test will be performed at screening and the EOS and ET Visits. Urine hCG testing will be performed at all other visits. If a urine hCG test is positive, a serum hCG test will be performed. Follicle-stimulating hormone level will be measured at screening to confirm postmenopausal state in women ≤ 55 years of age.

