APPENDIX B: CLINICAL LABORATORY ANALYTES

Serum Chemistry Panel

Alanine aminotransferase (ALT)	Gamma-glutamyl transferase
Albumin	Glucose
Alkaline phosphatase	Lactate dehydrogenase
Amylase	Potassium
Aspartate aminotransferase (AST)	Sodium
Blood urea nitrogen	Total bilirubin [1]
Calcium	Total protein
Creatine kinase (CK)	Uric acid
Creatinine	
CK-muscle/brain	
Estimation of glomerular filtration rate by the Modification of Diet in Renal Disease formula	
1. If >upper limit of normal, add conjugated (direct) bilirubin.	

Additional Chemistry Parameters

Alpha 2 macroglobulin	Ferritin
Autotoxin	Phosphate
Cardiac troponin I	

Efficacy Parameters

ALT	Adiponectin
AST	Cytokeratin-18
AST/ALT ratio	Interleukin 6
Iron-corrected T1	Fibronectin
High sensitivity C-reactive protein	Procollagen type III N-terminal peptide
Tumor necrosis factor alpha	Pro-C3
Chitinase-3-like protein 1 (also known as YKL-40)	Tissue inhibitor of metalloproteinases-1 (and derived enhanced liver fibrosis score)
Hyaluronic acid	

Pharmacodynamic Parameters

7 α hydroxy-4-cholesten-3-one	Fibroblast growth factor 19
Total bile acids	Chenodeoxycholic acid [1]
Deoxycholic acid [1]	Lithocholic acid [1]
1. Plasma levels of total, primary, and secondary bile acids may be assessed as appropriate.	

Lipid and Metabolic Profile

Branched-chain amino acid concentrations [1]

Hemoglobin A1c

Homeostatic model assessment for insulin resistance (morning fasting glucose and insulin)

Lipoprotein insulin resistance index by nuclear magnetic resonance based on serum cholesterol, high-density lipoprotein cholesterol, low-density lipoprotein (LDL) cholesterol, triglycerides, apolipoprotein B, small dense-LDL, and lipoprotein(a)

Lipoprotein particle size

Small LDL particle number

Small very low-density lipoprotein (VLDL) particle number

VLDL size

1. Liver function test.

Endocrinology

Human chorionic gonadotropin (hCG) [1]

Free triiodothyronine

Thyroid-stimulating hormone

Follicle-stimulating hormone (FSH) [2]

Free thyroxine

1. Serum hCG pregnancy test at screening and at study exit (whether at the End of Study or Early Termination Visit). Only urine hCG tests will be performed at all other study visits. If the urine hCG test is positive, pregnancy will be confirmed by a serum hCG test.
2. FSH level will be measured at screening to confirm postmenopausal state in women ≤55 years of age.

Coagulation

Activated partial thromboplastin time

Fibrinogen

International normalized ratio

Prothrombin time

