- Search for alternative causes to cardiac or muscular toxicity, ie, stroke, pulmonary infarction, dermatomyositis, polymyositis, convulsions, hypothyroidism, delirium tremens, or muscular dystrophies.
- If cardiac origin and rhabdomyolysis is ruled out and CK $<5 \times$ ULN, monitor CK every week until levels return to normal.
- If cardiac origin, rhabdomyolysis, or CK $\geq 5 \times$ ULN, discontinue the study drug and monitor weekly; consider referral/hospitalization.

For patients who experience a statin-related serious adverse event, collect pharmacokinetic blood samples for statin plasma concentration.

Causality of muscular adverse events will be adjudicated by the Sponsor or designee using the Statin-Associated Muscle Symptom Clinical Index.¹

¹ Rosenson RS, Miller K, Bayliss M, et al. The Statin-Associated Muscle Symptom Clinical Index (SAMS-CI): revision for clinical use, content validation, and inter-rater reliability. *Cardiovasc Drugs Ther.* 2017;31(2):179-186. DOI: 10.1007/s10557-017-6723-4.

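### In Part B a statin titrated at Day 28 has no scheduled CK for up to 28 days; adding CK to the existing Day 42 sample would cut this to at most 14 days

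*Protocol*

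**What the plan says.** **Statin rule.** Protocol Section 5.6.2 covers two groups and is not limited to one part of the study.

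- No statin at baseline, and a Day 14 LDL-C at least 25% higher than on Day 1: the instruction is "rosuvastatin 20 mg QD will be introduced and titrated up to 40 mg QD at the following visit if LDL-C remains". The threshold for the second step is an LDL-C still 5% over baseline.
- On a statin at baseline, and a Week 2 rise in LDL-C of more than 10 mg/dL: here "the statin dose may be increased and titrated up at the following visit if the LDL-C remains 5% above the baseline value".

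**Laboratory schedule, Part B.** CK belongs to the serum chemistry panel (Appendix B). Day 28 has the full set: "Chemistry, hematology, coagulation, and lipid and metabolic profile" (Section 6.3.3.3). Days 14 and 56 have the same. Day 42 has only "Chemistry for assessment of ALT, AST, ALP, GGT, and total bilirubin" (Section 6.3.3.4). Table 8 footnote p confirms it: "On Days 42 and 70 only ALT, AST, ALP, GGT, and total bilirubin will be measured". SAP Section 3.7.3 repeats this restriction.

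**Role of CK.** Section 9.8 states: "The safety of statin coadministration will be assessed at study visits specified in Appendix A by monitoring CK levels". Section 3.2 lists CK of at least 5 × ULN among the events for which dosing may be stopped. The Appendix E instruction for a CK at or above 5 × "ULN, discontinue the study drug and monitor weekly; consider referral/hospitalization" is to the same effect.

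**The concern.** The protocol itself prescribes a statin start and a dose increase during treatment, and it names scheduled CK as the monitor for statin coadministration. In Part B, however, the second dose step falls at the start of the longest stretch without CK up to that point in treatment. The smaller step, a 20 mg start after Day 14, is followed by a CK about 14 days later. The step to 40 mg is followed by one only after 28 days. A CK drawn at the Day 28 visit does not help, because it precedes any effect of the higher dose.

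At stake is the individual patient with a silent CK rise after titration. Until Day 56 no scheduled test would reveal that the 5 × ULN criterion had been met. Blood is drawn at Day 42 in any case.

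**Working it through.** The documents state no interval between titration and CK, so there is no planned figure to reproduce. The check is visit-day subtraction.

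**Inputs**
- Part B treatment visits: Days 1, 14, 28, 42, 56, 70, 84 (Section 3.1). The visit after Day 14 is Day 28.
- Part B scheduled CK from Day 1 on: Days 1, 14, 28, 56, 84, and follow-up at Day 98 (Sections 6.3.3 and 6.4, Appendix B).
- Part A scheduled CK includes Days 14, 21, 28 and 56 (Sections 6.3.1 and 6.3.2). The visit after Day 14 is Day 21.
- Visit window: 3 days either side at each visit concerned (Section 6).

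**Interval = next scheduled CK day − titration day.** Shortest: (CK day − 3) − (titration day + 3). Longest: (CK day + 3) − (titration day − 3).

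| Case | Nominal | With windows |
|---|---|---|
| Part B as planned | 56 − 28 = 28 days | 53 − 31 = 22 to 59 − 25 = 34 |
| Part B with CK at Day 42 | 42 − 28 = 14 days | 39 − 31 = 8 to 45 − 25 = 20 |
| Part A as planned | 28 − 21 = 7 days | 25 − 24 = 1 to 31 − 18 = 13 |

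**Delay in acting on the LDL-C result.** The deciding LDL-C is drawn at the Day 28 visit and no turnaround time is given. If the dose changes *d* days after Day 28, the planned interval is 28 − *d*. With CK at Day 42 it is 14 − *d*, for *d* below 14. If titration waits for the Day 42 visit, the interval is 56 − 42 = 14 days with or without the change.

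**Patients exposed to the gap.** The rates here are assumptions and do not come from the documents. Take half of the 90 Part B patients as baseline statin users (Section 1.2.2 reports more than 50% on stable statins in Part A). That gives 45 users and 45 non-users, each split into 30 active and 15 placebo.
- Non-users started on rosuvastatin, assuming 5–30% of active and 0–5% of placebo: 30 × 0.05 + 15 × 0 = 1.5, to 30 × 0.30 + 15 × 0.05 = 9.75.
- Users with the dose raised, assuming 10–40% of active and 0–20% of placebo: 30 × 0.10 + 15 × 0 = 3, to 30 × 0.40 + 15 × 0.20 = 15.
- Titrated at Day 28, assuming 25–75% of both: (1.5 + 3) × 0.25 = 1.1, to (9.75 + 15) × 0.75 = 18.6.
- Asymptomatic CK of at least 5 × ULN in the interval, assuming 0.1–1%: 1.125 × 0.001 = 0.001, to 18.56 × 0.01 = 0.19 patients.

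**How the SAP would treat a Day 42 CK.** SAP Section 3.1.4 puts CK in window Group II, whose Week 4 window is Days 22–42 and Week 8 window Days 43–70. There is no Week 6 row. A CK taken at the Day 42 visit would fall in one of these two windows and give way to the value labelled Day 28 or Day 56.

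**The case against.** The case for leaving the schedule alone is substantial.

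- **Other safeguards exist.** Muscle symptoms trigger an immediate CK work-up (Appendix E). Adverse events are assessed at Day 42. Muscle-related events are of special interest and must be reported within 24 hours (Section 9.1.4). Section 5.6.3 asks for close monitoring of any change in concomitant dosing, and investigators may add tests. A persistent transaminase rise at Day 42 prompts close observation with a drug history. All of this stands, and it narrows the gap to an asymptomatic rise that begins after the Day 28 sample. But none of these provisions schedules a CK for such a patient, and CK is not named among the close-observation steps for liver signals.
- **Entry limits.** Exclusion 20e keeps out statin users with CK above ULN. This protects baseline users. A non-user may enter with CK up to 3 × ULN and later be started on rosuvastatin.
- **No muscle signal.** Section 1.2.2 reports no CK increase in Part A. That is reassuring, though it rests on stable statin therapy rather than on new starts or titrations.
- **The 28 days is an upper figure apart from visit windows.** It assumes same-day action on the Day 28 LDL-C. This is correct, and the interval shortens with any delay.
- **The secondary objective does not depend on it.** A reader might infer that the missing CK undermines the assessment of safety with statin coadministration. The documents do not support that. Section 10.2.4.1 assesses the objective by comparing TEAE frequency between groups, and CK, one laboratory input among several endpoints, is still measured at Days 14, 28, 56, 84 and 98.

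**Conclusion.** The point holds as a minor design improvement. In Part B the first scheduled CK after a Day 28 titration comes up to 28 days later (22 to 34 with windows). With CK at Day 42 it would come after at most 14 days (8 to 20 with windows). Part B also lengthened this interval relative to Part A: read literally, the Part A titration visit is Day 21 and CK follows 7 days later. Part A does have a 28-day stretch without CK after Day 28, but it follows a titration only if the dose change was delayed to Day 28.

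Two stronger readings should be resisted. One is that titrated patients go four weeks without muscle monitoring. They do not, since only asymptomatic rises lack a scheduled test. The other is that the plan is in error. No provision is contradicted, and the documents require no particular CK interval after a statin change.

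The schedule figures follow directly from the visit days. The patient numbers (1.1 to 18.6 facing the gap, 0.001 to 0.19 with a silent CK of at least 5 × ULN) rest wholly on assumed rates and show only that the expected count is below one. The gain is in individual patient safety, not in the analysis.

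**What to change.** Add CK to the Day 42 sample in Protocol Section 6.3.3.4 and amend Table 8 footnote p to match, at least for patients whose statin was started or raised on study. Day 70 need not change, because no protocol titration step falls at Day 56.

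In SAP Section 3.1.4, give CK a Week 6 analysis visit so that by-visit summaries keep the value. Bring SAP Section 3.7.3 into line.

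The cost is one more analyte on blood already drawn, with no new visit or draw, and a few lines of text. The downside is an occasional repeat test for an incidental CK rise. SAP Section 4.1 records the Part B interim analysis as completed in February 2021. If Part B dosing has finished, the change is still worth carrying into the pivotal study that Section 1.1 expects these results to support.
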